3.4.3 Other Study procedures

At the first and last treatment visits, subjects will be asked to allow sampling of their tear fluid (6-10 µl) for laboratory assays. Tears will be collected from the lower lid tear meniscus and inferior fornix using a blunt glass microcapillary tube. In subjects with severe tear deficiency, a drop of preservative-free artificial tears will be instilled in the eye and conjunctival washings will be collected after a 2-minute period. Assays for eDNA abundance will be performed in Pl's laboratory using the Quant-iT™ PicoGreen® dsDNA Assay Kit as we described previously.²⁵ Number of cells in tear fluid will be counted using an automated cell counter.

Also, Schirmer test strips that are discarded after the Schirmer I test will be used to make impressions on glass slides and immunofluorescence staining will be performed in Pl's laboratory.²⁴ Five random 20x fields will be imaged using an inverted microscope and analyzed. eDNA strands will be traced and lengths calculated using Neurolucida software.

4 Subject Selection and Withdrawal

4.1 Inclusion Criteria

The PI and other members of International Chronic Ocular GVHD Consensus Group have established the consensus diagnostic criteria and classification for chronic ocular GVHD.⁴⁰

Table 1: Severity scale in chronic ocular GVHD

Severity scores (points)	Schirmer's test (mm)	CFS (points)	OSDI (points)	Conj (points)
0	>15	0	<13	None
1	11–15	<2	13–22	Mild/Moderate

Severity scores (points)	Schirmer's test (mm)	CFS (points)	OSDI (points)	Conj (points)
2	6–10	2–3	23–32	Severe
3	≤5	≥4	≥33	

CFS; corneal fluorescein staining, OSDI; Ocular Surface Disease Index. Conj; conjunctival injection. Severity classification; Total score (points); (Schirmer's test score+ CFS score+ OSDI score+ Conj injection score) = None;0–4, Mild/Moderate; 5–8, Severe, 9–11.

Table 2: Diagnosis of chronic ocular GVHD

	None (points)	Probable GVHD (points)	Definite GVHD (points)
Systemic GVHD(-)	0–5	6–7	≥8
Systemic GVHD(+)	0–3	4–5	≥6

Based on these criteria (Tables 1 and 2),⁴⁰ patients with definite ocular GVHD will be enrolled. Additionally, all of the following criteria should be met to be eligible for the study:

- Aged 18 years or older.
- Capable of giving informed consent and does provide informed consent.
- Schirmer I <10
- Corneal/ conjunctival (Fluorescein and Lissamine Dye) staining ≥1
- Ocular symptoms must be considered as annoying or activity limiting (OSDI ≥13; mild).
- Women must be post-menopausal ≥ 1 year, or surgically sterilized. If not, a negative urine pregnancy test is required within 14 days of receiving her first dose of test medication (placebo/ study drug) along with definite evidence of contraceptive use during the duration of the study. Women of reproductive age should use a method of birth control that is acceptable to the subject and the study doctor. This may include oral contraceptive pills, birth control implants, barrier methods or abstinence. If a subject mentions she suspects she may be pregnant after being enrolled, another pregnancy test will be administered. If the test is positive, she will be discontinued from the study immediately.

4.2 Exclusion Criteria

Subjects will not be eligible for the study if any of the following criteria are met:

- Allergic to rhDNase I or any similar products, or excipients of rhDNase I eye drops 0.1%.
- Receiving or have received within 30 days any experimental systemic medication.
- Active ocular infection or ocular allergies.
- Any history of eyelid surgery or ocular surgery within the past 3 months.
- Corneal epithelial defect larger than 1 mm² in either eye.

•

- Have active drug/alcohol dependence or abuse history.
- Vulnerable populations, such as neonates, pregnant women, children, prisoners, institutionalized individuals, or others who may be considered vulnerable populations.

Participants will be permitted to continue their chronic GVHD treatments, including the use of artificial tears, eyelid massage, or warm compresses. Subjects wearing contact lenses (Soft bandage contact lenses or PROSE lens) will be asked to discontinue contact lens wear for 1 month prior to being

enrolled (Baseline visit) and will be required to not wear contact lenses for the duration of the study (until week 10 visit).

4.3 Subject Recruitment and Screening

Potential subjects will be recruited from the clinical practice of the investigator at the time of their routine eye examination visit. The clinical practice is located in the Illinois Eye and Ear Infirmary, Department of Ophthalmology and Visual Sciences, University of Illinois at Chicago (UIC). Subjects will include patients who have been diagnosed with oGVHD in the investigator's eye clinic (cornea clinic or the comprehensive eye clinic), in the Illinois Eye and Ear Infirmary. Patients diagnosed with oGVHD, and willing to enter the study, may be referred to the PI's clinic by other ophthalmologists at UIC, as well as the ophthalmology departments at Loyola University Chicago, University of Chicago, and Northwestern University. These centers will be provided with 'information sheets' to provide to subjects before they come to the PI's clinic. Although patients may be referred from these sites, no study procedures, including enrollment will be performed at any site, other than the PI's clinic in Illinois Eye and Ear Infirmary. All subjects will be will be screened, recruited, and will attend all study related visits only at the PI's clinic in Illinois Eye and Ear Infirmary.

Patients with definite ocular GVHD (with Schirmer I <10 and annoying or activity limiting visual symptoms) will be approached by a member of the research staff to determine if the subject might be interested in participating in a research study. If the subject is interested, the research staff member will describe the study. If the subject is willing to enter the study, the subject will be asked to review the study consent form, the PI will meet with the subject to review the form, the study will be discussed to confirm the subject's understanding of the study, and to answer any questions that the subject might have. Once the subject demonstrates understanding of the study and agrees to participate in the study, the subject will be asked to sign the informed consent form in the presence of the PI. Consent will be obtained prior to screening to determine eligibility. Screening procedures include documentation of definite oGVHD as well as other assessments as detailed in section 6.5.1. Eligible subjects will be enrolled in the study.

4.4 Early Withdrawal of Subjects

4.4.1 When and How to Withdraw Subjects

Subjects have the right to withdraw from the study at any time, for any reason, without jeopardizing their medical care. Where possible, subjects will be followed for safety and encouraged to return for follow-up visits for any unresolved safety events.

The IRB and Investigator also have the right to withdraw subjects from the study for the following reasons: when continuation may jeopardize the health of the subject, protocol violations, adverse events or concurrent conditions, administrative or other reasons.

4.4.2 Data Collection and Follow-up for Withdrawn Subjects

If a subject withdraws from the study prior to 8 weeks, the subject will be asked to complete the procedures outlined in the 10 week visit as well as the Test Substance Tolerance scale from 8 weeks, as soon as possible. Subjects who voluntarily withdraw from the study between 8 weeks and 10 weeks will be asked to complete procedures outlined in the 10 weeks visit as soon as possible. Subjects who

are withdrawn due to adverse events will be followed at least until resolution or stabilization of the adverse event.

If the subject remains in the study for safety evaluation, follow-up visits will be scheduled according to the schedule of visits and procedures found in the synopsis.

5 Study Drug

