	8.5.		
	8.6	ADVERSE EVENT REPORTING	
	8.6.		
	8.6.		
	8.6.	-	
	0.0.	8.6.3.1 FOLLOW-UP INFORMATION	
	8.7	STUDY CLOSE-OUT	
	8.7		
	0.7	8.7.1.1 7 CALENDER DAY TELEPHONE OR FAX REPORT.	
		8.7.1.2 15 CALENDER DAY WRITTEN REPORT	
	8.8	FAX NUMBER FOR IND SAFETY REPORTS.	
	8.9	IN CASE OF EMERGENCY	
	8.10	DATA SAFETY MANAGEMENT PLAN	
	8.11	STUDY OVERSIGHT	_
	8.12	REPORTING CHANGES IN STUDY STATUS	
9	DAT	A QUALITY AND SAFETY REVIEW PLAN AND MONITORING	39
	9.1	DATA QUALITY AND MANAGEMENT	39
	9.1	-	
	9.1		
	9.2	SUBJECT ACCRUAL AND COMPLIANCE	
	9.2		

	9.2	2.2 MEASUREMENT AND REPORTING OF PARTICIPANT ADHERENCE TO TREATMENT PROTOCOL	40
g	9.3	STOPPING RULE	40
	9.4	DATA AND SAFETY MONITORING BOARD (DSMB)	40
	9.4		
9	. 5	SAFETY REVIEW PLAN	41
10	CON	NFIDENTIALITY	41
11	sou	JRCE DOCUMENTS	42
1	1.1	RECORDS RETENTION	42
12	ETH	ICAL CONSIDERATIONS	42
13	STU	DY FINANCES	
1	3.1	FUNDING SOURCE CONFLICT OF INTEREST	43
1	3.2	CONFLICT OF INTEREST.	43
1	3.3	SUBJECT STIPENDS OR PAYMENTS	43
14	REF	ERENCES	44
15	APP	ENDIX I	47

SCHEDULE OF VISITS AND PROCEDURES

	gı	(e)	(es)					
	Screening	Day 1 (Pre-Dose)	Day 1 (Post-Dose)	Week 2	Week 4	Week 6	Week 8	Week 10
Informed consent	Х							
Demographic information	Χ							
Medical history/ Con Meds/ Transplant history	Х							
Ophthalmic/ oGVHD history	Χ							
Vital signs		Х		Χ	Χ	X	Χ	Х
Best Spectacle Corrected Visual Acuity		Х						Х
Ocular Surface Disease Index (OSDI)	X	Х		Χ	Χ	X	Χ	Х
Clinical Global Impression (CGI)				Χ	Χ	Х	Χ	Х
Subject Global Assessment (SGA)				Χ	Χ	Χ	Χ	Х
Visual Analogue Scale (VAS)			Х	Х	Х	Х	Х	
Ophthalmic examination (Slit lamp)	Χ	Х		Χ	Χ	Х	Χ	Х
Schirmer 1 test and Fluorescein and Lissamine Dye staining	Х	Х					Х	
Ocular surface Redness (OR) score		Х		Χ	Χ	Χ	Χ	Х
Tear fluid analysis (PicoGreen, Cellometry)		Х					Χ	
Keratograph Oculus Redness Score		Χ			Χ		Χ	
Non-invasive Keratography Tear Film Break-up Time (NIKBUT)		Х			Χ		Χ	
Tear Meniscus Height (TMH)		Χ			Χ		Χ	
TearLab Osmolarity Test		Х			Χ		Χ	
InflammaDry for MMP-9 Protein		Х			Х		Х	
Pregnancy test (urine)*	Х							
Randomization visit		Х						
First study medication		Х						
Drug dispensation visits			Х	Х	Х	Х		
Instruction on study medication self- administration			Х	Х	Х	Х		

Version: 10.0; 07-26-2018

Physical inspection of nose & oropharynx	Х		Х	Х	Х	Х	Х
Adverse Events/ Concomitant Medications	Х	X++	Х	Х	Х	Х	Х
Conjunctival culture**	Х					Х	

^{*}If applicable ++ AEs only

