3.2 Primary Study Endpoints

Primary Efficacy End Point: The primary end point is a mean reduction in corneal staining score after 8 weeks of treatment, as measured by Fluorescein and Lissamine dye staining.

Primary Tolerability End Point: The change in the test substance tolerance between Day 1 (post-dose) and at weeks 2, 4, 6 and 8.

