3.3 Secondary Study Endpoints

The secondary study endpoints will include:

- 1. The change in the Ocular Surface Disease Index (OSDI) which is a patient's subjective rating scale
- 2. Change in tear secretion as measured by Schirmer I test
- 3. The proportion of eyes achieving complete corneal staining clearance after treatment
- 4. Change in conjunctival surface staining score as measured by Fluorescein and Lissamine dye staining
- 5. The change in subjective ocular surface redness score (OR) using the validated bulbar redness (VBR) grading scale
- 6. Visual acuity change
- 7. Change in frequency of administration of artificial tears or concomitant eye drops
- 8. Change in number of corneal filaments (slit-lamp examination)
- 9. Change in amount of mucoid films (slit-lamp examination)
- 10. Clinical Global Impression (CGI) of change in symptoms from baseline (physician's rating)
- 11. Subject Global Assessment (SGA) of overall change from baseline (subject's rating)
- 12. Change in Non-Invasive Keratograph Tear Break-Up Time (NIKBUT)
- 13. Change in Tear Meniscus Height (TMH)
- 14. Change in Keratograph Ocular Bulbar Redness Score
- 15. Change in MMP-9 Protein Detection
- 16. Change in Tear Fluid Osmolarity
- 17. Change in eDNA abundance in tear fluid
- 18. Change in tear fluid cell count
- 19. Change in eDNA strand length on Schirmer test strip impressions

Corneal filaments are mucous tags that are adherent to the surface of cornea. Mucoid films are mucous collections accumulating on the surface of the eye. The number of such mucus tags/ filaments will be counted on each clinical examination (slit-lamp examination).

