Contact lenses, commonly used to treat oGVHD, will be withheld during the course of this study. This is necessary as the proposed primary efficacy outcome measure is corneal Fluorescein and Lissamine Dye Staining. Contact lenses can directly reduce corneal SPK and staining due to ensconcing and acting like a bandage that prevents corneal exposure to tear fluid inflammatory materials. Thus, because of over lapping effects on the primary outcome measure, it may not be possible to attribute any observed clinical benefit to rhDNase I treatment if contact lenses are used concurrently. This approach has been used in other clinical trials that have investigated the use of an anti-inflammatory agent in dry eye disease (NIH funded 'Dry Eye Evaluation and Management (DREAM) study').⁴¹

Stopping contact lens wear may increase the risk of worsening of oGVHD during the wash-out period and during the course of the study. However, because other eye drop treatments will continue during

the wash out period as well as during the course of the study, we do not expect any significant clinical worsening during the study. We do however expect the frequency of use of artificial tears to go up during the wash out period and during the course of the study.

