6.5.6 Visit 6: Week 8 (± 2 days)

Treatment Visit (after any dose for that day)

- Vital Signs
- OSDI
- Fluorescein and Lissamine Dye staining, and Schirmer 1 test
- Keratograph Oculus Redness Score
 - > Non-invasive Keratography Tear Film Break-up Time (NIKBUT)
 - > Tear Meniscus Height (TMH)
- TearLab Osmolarity Test
- InflammaDry Test for MMP-9 Protein
- Clinical Global Impression, Subject Global Assessment
- Test Substance Tolerance (VAS)
- Ophthalmic Examination (slit lamp examination, Ocular surface redness score)
- Tear fluid collection for analysis (PicoGreen, Cellometry)
- Physical Inspection of the Nose and Oropharynx
- Conjunctival and eyelid margin cultures
- Review the subject's diary and record changes in concomitant medication, deviations from drug schedule and adverse events.

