6.5.7 Visit 7: Week 10 (± 2 days)

Follow-Up Visit

- Vital Signs
- BSCVA (Snellen's chart)
- OSDI
- Clinical Global Impression, Subject Global Assessment
- Ophthalmic Examination (slit lamp examination, Ocular surface redness score)
- Physical Inspection of the Nose and Oropharynx
- Record changes in concomitant medication and adverse events.

7 Statistical Plan

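### The early-withdrawal visit omits corneal staining, so a subject who leaves before week 8 and is seen only there has no post-baseline value of the primary efficacy measure; secondarily, the 25% missing-value rule has no stated denominator

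*Combined protocol and SAP*

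**What the plan says.** **Primary measure.** Section 3.2 defines the primary efficacy endpoint as the mean reduction in corneal staining score "after 8 weeks of treatment, as measured by Fluorescein and Lissamine dye staining". Section 5.6 confirms that "the proposed primary efficacy outcome measure is corneal Fluorescein and Lissamine Dye Staining". Section 3.3.1 scores the cornea in five zones, each graded 0 to 3, with fluorescein.

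**When it is measured.** The row "Schirmer 1 test and Fluorescein and Lissamine Dye staining" in the schedule table is marked at screening, Day 1 pre-dose and week 8. The visit lists in 6.5.1 to 6.5.7 agree. Week 8 lists "Fluorescein and Lissamine Dye staining, and Schirmer 1 test"; weeks 2, 4, 6 and 10 list no staining. The only eye examination entry at week 10 is "Ophthalmic Examination (slit lamp examination, Ocular surface redness score".

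**Withdrawal before week 8.** Section 4.4.2 says "the subject will be asked to complete the procedures outlined in the 10 week visit as well as the Test Substance Tolerance scale", the latter being the week 8 tolerability rating. It adds that a subject who stays on for safety follow-up is seen on the regular schedule. Section 5.7 says that stopping study drug or going back to contact lenses means withdrawal from the study.

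**Missing data.** Section 7.2 (repeated in the Study Summary) applies intent-to-treat to efficacy and compares arms over time with a mixed model. It uses multiple imputation when less than 25% is missing and otherwise leaves the item out. It does not say what the 25% is counted over, or whether a variable or a subject is left out.

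**The concern.** Section 4.4.2 restores one primary measure that the week 10 list lacks, the tolerability VAS, but not the other, corneal staining. No reason is given. The subject is already asked to attend a slit-lamp visit at which staining could be done.

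If staining is not done there, the mixed model has only pre-treatment staining from that subject. Any imputed week 8 score must then rest on baseline staining and on other measures such as OSDI, redness, the global ratings and slit-lamp signs. Because stopping study drug leads to withdrawal, the gap falls on subjects whose absence may be related to how they fared, in an analysis meant to follow intent-to-treat.

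The 25% rule is a separate matter. As written, it leaves open, until the data have been seen, whether the primary endpoint or particular subjects drop out of the analysis.

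**Working it through.** **1. Staining against visits** (schedule table; sections 6.5.1 to 6.5.7)

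| Visit | Slit lamp | Dye staining |
|---|---|---|
| Screening | yes | yes |
| Day 1 pre-dose | yes | yes |
| Weeks 2, 4, 6 | yes | no |
| Week 8 | yes | yes |
| Week 10, also used for withdrawal before week 8 | yes | no |

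Post-baseline staining assessments for a subject seen only at the withdrawal visit: 0.

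**2. Secondary endpoints with the same gap** (numbered as in section 3.3)

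- Measured after baseline at week 8 only: nos. 2, 3, 4, 17, 18, 19 = 6. These are Schirmer I, complete clearance ("The proportion of eyes achieving complete corneal staining clearance after treatment"), conjunctival staining, tear eDNA, tear cell count and eDNA strand length. For tear fluid, section 3.4.3 says "At the first and last treatment visits, subjects will be asked to allow sampling of their tear fluid"; strand length uses the Schirmer strips.
- Weeks 4 and 8 only: nos. 12 to 16 = 5.
- Also captured at week 10: nos. 1 and 5 to 11 = 8.
- Check: 6 + 5 + 8 = 19.

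**3. The plan's sample size.** Section 7.1 gives means of 3.1 and 1.24 (difference 1.86), SD 2.5, two-sided alpha 0.05 and 80% power. An exact two-sample t calculation gives 30 per group (power 80.9%), which reproduces the stated figure. Enrolling 36 leaves room for 36 − 30 = 6 per arm, or 6/36 = 16.7%. The protocol does not call this a dropout allowance, so it is only one assumed rate below.

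**4. Weight of one subject.** 1/36 = 0.028. An imputation error of one point in one subject moves that arm's mean by 0.028 points.

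**5. The 25% rule when 18 of 72 subjects lack week 8 staining**

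| What the percentage is taken over | Missing | Consequence |
|---|---|---|
| Week 8 staining values | 18/72 = 25.0% | not below 25%: primary endpoint left out |
| Baseline plus week 8 staining values | 18/144 = 12.5% | imputed |
| Screening, baseline and week 8 staining values | 18/216 = 8.3% | imputed |
| Each subject's own staining values | 1/3 = 33.3% or 1/2 = 50% | each of the 18 subjects dropped |

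**6. How likely the trigger is.** Dropout rates are assumed and subjects are treated as independent.

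- *Per variable and per visit.* The trigger is 18 of 72, since 17/72 = 23.6% is still below 25%. P(X ≥ 18), X binomial with n = 72:

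| Assumed dropout | 10% | 15% | 16.7% (6/36) | 20% | 25% |
|---|---|---|---|---|---|
| Probability | 0.02% | 1.8% | 4.6% | 17.9% | 54.5% |

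- *Over the 144 values.* The trigger is 36 of 72 subjects (36/144 = 25.0%; 35/144 = 24.3%). P(X ≥ 36) is about 4 × 10⁻⁶ even at 25% dropout.

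**7. Does adding withdrawal-visit staining settle the 25% rule?** No. On the per-subject count, one missing value of four is 1/4 = 25.0%, still not below 25%.

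**The case against.** **The effect is small.** Against the planned difference of 1.86, one subject wrong by one point is 0.028/1.86 = 1.5%. Six subjects in one arm, all wrong by one point in the same direction, give 6/36 = 0.167, or 9.0%. The planned difference is on the RBS score, so this comparison is only illustrative. The objection stands as a limit on the claim. A reader might infer that the omission biases the primary result, or does so in a known direction. The documents do not support that: they give neither a dropout rate nor the reasons for dropout by arm.

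**The cornea is still examined.** Section 3.4.2 has superficial punctate keratopathy and filaments recorded at every slit-lamp examination, including the withdrawal visit. This narrows the gap, but it is not the five-zone score of section 3.3.1.

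**An off-schedule value is not a week 8 value.** True. Adding it informs the imputation and does not recover the endpoint. Nor is measuring staining at only one post-baseline visit a fault in itself, since the endpoint needs only baseline and week 8.

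**Withdrawn subjects may stay on schedule.** Section 4.4.2 allows this for safety follow-up, so the point is confined to subjects seen only at the withdrawal visit. A reader might infer that every subject who worsens loses the primary outcome. That goes too far: two of the three responses listed in section 5.7, more artificial tears and more anti-inflammatory therapy, do not end participation.

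**The 25% rule may never bite.** A reader might take 54.5% as the chance that the rule removes the primary endpoint. That figure needs both an assumed 25% dropout and a count per variable and per visit. Since section 7.2 models outcomes over time, a count over all staining values is equally open, and on it the chance is negligible. What stands is the ambiguity, not a likely loss.

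**Conclusion.** The main point holds on the text. A subject who leaves before week 8 and is seen only at the withdrawal visit has no post-baseline corneal staining, and 6 of 19 secondary endpoints share the gap. This rests on the schedule table and the visit lists, which agree, and on no assumption about dropout. It is an inexpensive improvement to data collection, not evidence of bias.

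The secondary point also holds, as an ambiguity: the same 18 missing subjects lead to exclusion of the primary endpoint, to imputation, or to loss of those subjects, depending on the denominator. Dropping subjects for lack of week 8 staining would conflict with the stated intent-to-treat principle. The trigger probabilities depend on assumed dropout rates and belong only to the reading named beside them.

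**What to change.** **Section 4.4.2.** For subjects leaving before week 8, add corneal fluorescein staining, conjunctival lissamine staining and Schirmer I to the withdrawal visit. Record the visit date and any contact lens use since the last dose, because section 5.6 says that lenses directly lower staining. Use the staining value as a predictor in the imputation, not as the week 8 value. Reconcile sections 4.4.2 and 5.7 on whether subjects who stop study drug remain under scheduled observation.

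*Cost:* the tests are already in the protocol and the visit is already requested. Expect a few minutes per withdrawn subject, and some off-schedule or lens-affected values.

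**Section 7.2 and the Study Summary.** State that the 25% exclusion does not remove the primary endpoint, or any randomised subject, from the primary analysis, and that missing week 8 staining is handled by the multiple imputation already planned. For other outcomes, state the denominator and what is left out when the threshold is reached.

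*Cost:* a text change. If much is missing, the primary result leans more on the imputation model.

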3.3.9 Tolerability End Point: Test Substance Tolerance (Visual Analogue Scale)

Subjects will assess their tolerance to the administration of the test medication (placebo/ study drug), utilizing a Visual Analog Scale (VAS). The VAS is a 100 mm horizontal line with verbal descriptors at either end. The VAS ratings will be completed after administration of the test medication on Day 1 (post-dose), week 2, week 4, week 6 and week 8. Subjects will place a single slash mark across the horizontal line between the end labeled "completely intolerable" (0 mm) and "easily tolerable" (100mm). The VAS rating is as follows:

Please rate the degree of comfort or lack of comfort associated with administering the eye drop by making one slash mark on the line below:

Visual Analogue Scale

On the scale of 0 to 100 seen below, please mark where you would rate your tolerability to administration of the test drug.

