5.7 Rescue Plan

The research staff, including the PI, will be masked to randomization, thus will not be aware if a particular subject receives study drug or placebo. Subjects will be monitored by the Principal Investigator at each study visit. Any worsening of oGVHD or any adverse event (AEs) will be recorded and in the case of AEs followed to resolution. In case of clinical worsening/ adverse event(s), based on the individual subject's clinical condition, one or more of the following therapeutic decisions may be implemented:

- (1) Increasing the frequency of artificial tears use,
- (2) Increasing the use of anti-inflammatory therapy (Restasis/ corticosteroids),
- (3) Discontinue the study drug.

The decision will be made by the Principal Investigator based on his clinical judgment and the individual subject's clinical condition. If contact lens wear is reinstituted and/or the study drug is discontinued, the subject will be withdrawn from the study. If an adverse event is severe enough to discontinue the subject from the study, the PI may decide to break the subject's randomization code if it seems relevant to the treatment of his/her ocular condition at that time. He/ She will receive the treatment required for his/ her eye condition as per established clinical guidelines.

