7.2 Statistical Methods

Biostatisticians from the Design and Analysis Core (DAC) of UIC-CCTS will perform the analysis. We will assess treatment efficacy based on the intent-to-treat principle using each participant's randomized treatment assignment to define treatment groups and outcomes. Safety variables will be analyzed with regard to treatment that participants actually received (the safety population). One eye (target eye) will be selected at screening visit for statistical comparisons as follows: (i) if only 1 eye meets inclusion criteria, this eye is used; (ii) if both eyes meet inclusion criteria, the eye with the higher RBS score is used; (iii) if both eyes have the same RBS score, then the one with the lower Schirmer I score is used; (iv) if both eyes have same scores, the right eye is used. Secondary analyses will be performed for the non-target eye as well. To assess the effect of treatment, we will compare each outcome measure between rhDNase I (study) vs. Vehicle (control) group over time using general linear mixed model, mixed-effects ordinal logistic regression, and mixed-effects multinomial logistic regression for continuous, ordinal and nominal variables respectively. Treatment, time and their interaction will be included in the model. Missing values of less than 25% will be imputed by using multiple imputations; otherwise will not be included in the analysis. Descriptive statistics will be utilized before the modeling to describe the sample. Assumptions behind each statistical method will be examined. Two-sided Pvalue less than 0.05 would be considered as statistical significance. All the analyses will be conducted by using SAS 9.2 (SAS Inst., Cary, NC).

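### The exit tolerability rating has no stated role in the primary VAS analysis, so ratings after an intolerance stop can be imputed close to those of subjects who continued

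*Combined protocol and SAP*

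**What the plan says.** All references are to the combined protocol and SAP.

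- Section 3.2 defines the primary tolerability endpoint as "The change in the test substance tolerance between Day 1 (post-dose) and at weeks 2, 4, 6 and 8".
- Section 3.3.9 ties each rating to a dose: "The VAS ratings will be completed after administration of the test medication on Day 1 (post-dose" and at the later treatment visits. The scale runs from 0 mm (worst tolerance) to 100 mm (best).
- Section 5.7 states: "If contact lens wear is reinstituted and/or the study drug is discontinued, the subject will be withdrawn from the study". Section 5.6 has the same rule.
- Section 4.4.2 asks a subject who leaves before week 8 for the week 10 procedures "as well as the Test Substance Tolerance scale from 8 weeks, as soon as possible". It adds: "If the subject remains in the study for safety evaluation, follow-up visits will be scheduled according to the schedule of visits and procedures".
- Section 7.2 gives the only missing-data rule: "Missing values of less than 25% will be imputed by using multiple imputations". At or above that limit the values are left out. No imputation model, missingness assumption or sensitivity analysis is given.
- Section 7.3 restricts the analysis population to subjects with two weeks or more of treatment and a week 2 visit. Section 7.2 separately describes intent-to-treat for efficacy and treatment received for safety. It does not say which applies to the tolerability VAS.
- Section 8.1 allows subjects who withdraw because of an adverse event to be replaced.
- Section 3.4 makes the proportion completing eight weeks of therapy the primary safety endpoint.

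**The concern.** Section 2 asks whether patients can tolerate the drops for eight weeks. The subjects who stop because they cannot are the most informative ones, and stopping ends their on-drug ratings by design. The plan collects one rating at exit but leaves three things open: which dose it rates, which visit it stands for, and whether it enters the analysis. For the remaining weeks the only rule is imputation below 25% missing.

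Under the usual missing-at-random form, imputation predicts a stopper's later ratings from his or her earlier ones, using relations learned mainly from subjects who continued. The result estimates what the rating would have been had the subject gone on tolerating the drops. The earliest stoppers do not reach imputation at all, because section 7.3 removes them. Both routes make the drops look better tolerated than they were, most of all in the arm with more intolerance.

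**Working it through.** **Plan figures.** The plan states no figure for the VAS. Its 30 per group (section 7.1) is for corneal staining and reproduces. With difference 3.1 − 1.24 = 1.86 and SD 2.5, the t test needs 29.35, rounded up to 30. For this point it matters only that 36 per arm are enrolled and that 36 against 30 leaves room for 1 − 30/36 = 16.7% loss, or 6 per arm. No dropout rate is stated.

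**Assumptions (none from the documents).** Mean VAS of stayers 80 mm, SD 15, correlation between visits 0.6; true tolerance T of stoppers 20 mm (range 0 to 40); all stoppers in one arm; stopping unrelated to the Day 1 rating.

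**Step 1: who is imputed.** The unit of the 25% is not defined.

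- By arm and visit: 9/36 is exactly 25%, so imputation applies to at most 8 stoppers.
- Over both arms: 18/72 is 25%, so at most 17.
- By subject, over five ratings and without an exit rating: a stop after week 6 loses 1/5 = 20% and is imputed; a stop after week 4 loses 2/5 = 40% and is left out.

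**Step 2: size if stoppers are filled in like stayers.** Overstatement of the arm mean = (k/36) × (80 − T).

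| Stoppers k | T = 0 | T = 20 | T = 40 |
|---|---|---|---|
| 2 | 4.4 mm | 3.3 mm | 2.2 mm |
| 4 | 8.9 mm | 6.7 mm | 4.4 mm |
| 6 | 13.3 mm | 10.0 mm | 6.7 mm |
| 8 | 17.8 mm | 13.3 mm | 8.9 mm |

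**Step 3: against the standard error.** A stayer's change has variance 2 × 15² × (1 − 0.6) = 180 (SD 13.4). A stopper scored at 20 mm has mean change −60 and variance 15² = 225.

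- With 4 of 36 stopping, the arm's variance is (8/9)(180) + (1/9)(225) + (1/9)(8/9)(60²) = 160 + 25 + 355.6 = 540.6 (SD 23.3). The SE of the difference is √(540.6/36 + 180/36) = 4.5 mm, and 6.7/4.5 is about 1.5 SE.
- With 6 of 36, the variance is 150 + 37.5 + 500 = 687.5. The SE is √(687.5/36 + 180/36) = 4.9 mm, and 10.0/4.9 is about 2.0 SE.

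**Step 4: does imputation behave this way?** A simulation used five visits, between-subject SD 12, within-subject SD 8 and ratings limited to 0–100. Stoppers left after week 2, when their rating had already fallen a quarter of the way to T. Later weeks were multiply imputed from arm and earlier ratings. Week 8 difference between arms, T = 20:

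| Stoppers | Exit rating | True | Estimated |
|---|---|---|---|
| 4 | not used | −6.4 mm | −0.5 mm |
| 4 | entered at week 8 | −6.5 mm | −6.5 mm |
| 6 | not used | −9.8 mm | −1.0 mm |
| 6 | entered at week 8 | −9.9 mm | −9.9 mm |

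Without the exit rating about nine tenths of the deficit disappears (1 − 1.0/9.8 = 90%). With it, the week 8 deficit is kept, because the simulation took the exit rating to equal true tolerance. Weeks 4 and 6 were not simulated with an exit rating present. An imputation model that used it as a predictor would recover part of the deficit there.

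**The case against.** The best reply is that the plan already collects the needed value. Taking the week 8 scale early reads naturally as an early week 8 rating, and the item asks about administering the drop, so it can be answered about the last dose. Entered at week 8, it protects that time point. This stands, and it rules out a stronger reading. A reader might infer that the arm's mean change to week 8 would come out near 0 mm however many subjects stop. That needs the exit rating to be missing or discarded, and nothing in the documents says to discard it.

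Other points also stand:

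- A reader might infer that each stopper gives exactly one off-drug rating. Section 4.4.2 lets a subject stay for safety evaluation on the visit schedule, which includes the VAS.
- A reader might infer that all stoppers are imputed. The earliest are excluded under section 7.3, and at 25% or more the values are left out.
- A reader might put 4 stoppers at about 2 SE (6.7/3.16, with 3.16 = 13.4 × √(2/36)). That SE ignores the stoppers' own spread; including it gives about 1.5.
- Missing at random is the usual form of imputation, not a stated choice.
- The completion endpoint in section 3.4 counts stoppers as non-completers, so discontinuation is not lost from the trial.

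None of this assigns the exit rating to an analysis or scores weeks 2 to 6 after a stop. The completion endpoint reports stopping alongside the VAS but does not correct it.

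**Conclusion.** The point holds as a gap in the analysis rule. The plan collects an exit VAS without giving it a role, leaves the other post-stop weeks to unspecified imputation or omission, and drops the earliest stoppers. Tolerability can therefore be overstated at the intermediate weeks, and at week 8 when the exit rating is missing or unused.

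In the illustration, 4 stoppers in one arm hide about 6.7 mm (about 1.5 SE) and 6 hide about 10 mm; over T = 0 to 40 mm the ranges are 4.4 to 8.9 and 6.7 to 13.3 mm. Every VAS value here is assumed, and stoppers split evenly between arms would bias both arm means but largely cancel in the difference. If the exit rating is entered at week 8 and reflects true tolerance, the week 8 bias is largely removed. The documents do not support the claim that the plan as written must erase intolerance; they leave open a choice on which that depends. The rule should be fixed before unblinding.

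**What to change.** - **Section 4.4.2:** state that the exit VAS rates the last dose taken, and record the date of the rating and of that dose.
- **Section 7.2, main analysis:** for a subject who stops because of intolerance or an adverse event related to the drops, use the observed exit rating for all visits after the stop, including week 8, in place of multiple imputation.
- **Section 7.2, sensitivity analysis:** score those same visits at 0 mm, the scale's own worst anchor. Use this score also where such a subject gave no exit rating.
- **Section 7.2, imputation:** keep it for missed visits and for exits unrelated to the drops. State the model and the unit of the 25% limit.
- **Section 7.3:** for tolerability, include every dosed subject with a Day 1 post-dose VAS, whatever the treatment duration or week 2 attendance, and whether or not the subject was replaced.
- **Case report form:** record the reason for every withdrawal. Sections 8.3 and 8.4 capture stops for adverse events, but section 4.4.1 allows exit for any reason.

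The cost is wording in three sections, a few form fields and one sensitivity analysis; treatment is unchanged. The downside is that the week 8 mean becomes partly a carried-forward value and may be less favourable. The spread also grows, in the illustration from an SD of change of 13.4 to 23.3 mm with 4 stoppers, so the comparison is less precise.
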